7.4.2 Treatment Regimen

Describe dose, route of administration and treatment duration. Include information about dose adjustments.

The devices will be utilized for a period of three months.

7.4.3 Method for Assigning Subject to Treatment Groups

Describe the randomization process and how the associated treatment assignment will be made.

Not applicable.

7.4.4 Subject Compliance Monitoring

Insert the procedures for monitoring subject compliance.

The database will be monitored daily for the participant's response to the sent messages and for heartrate measured by the Fitbit Versa. Any participant that has not responded to any sent messages or has not recorded a heartbeat over a three-day period will be contacted by a study team member. The research team will assure that no safety or study issues have occurred and that the participant wishes to continue with the study procedures.

7.4.5 Blinding of the Test Article

Describe how the test article is blinded.

Not applicable.

7.4.6 Receiving, Storage, Dispensing and Return

7.4.6.1 Receipt of Test Article

Describe how the test article will be obtained and from what source. Describe how the study test article will be packaged along with amounts (e.g., number of tablets/capsules or volume of liquid) and labeling. If drug kits are used, describe all the contents of the kit and associated labeling.

The Fitbit Versa and the H2O Pal will be purchased from their commercial manufacturers.

7.4.6.2 Storage

Describe the plans to store, handle the test article so they will be used only on subjects and only by authorized investigators. Describe storage temperature requirements and how temperature will be monitored and recorded.

Not applicable.

7.4.6.3 Preparation and Dispensing

Describe how the test article will be assigned to each subject and dispensed. Describe the steps necessary to prepare the test article. Include where the test

article preparation will be done and by whom. Fully describe how the study treatment is to be administered and by whom.

The H2O Pal and Fitbit Versa will be linked with the participant's smartphone via apps. The devices will be prepared and linked during Visit 1 (training session) for the participant by the research study team.

7.4.6.4 Return or Destruction of the Test Article

Describe the procedures for final reconciliation of the test article supply at the end of the study and whether the test article is to be shipped back to a source or destroyed on site.

The participant will keep the H2O Pal water bottle upon study completion. The participant will be asked to return their Fitbit Versa at Visit 3, upon completion of the study.

7.4.6.5 Prior and Concomitant Therapy

Describe what prior and/or concomitant medical therapy will be collected. Describe which concomitant medicines/therapies are permitted during the study. Describe which concomitant medicines are not permitted during the study.

Not applicable.

8.0 Subject Numbers and Statistical Plan

8.1 Number of Subjects

Indicate the total number of subjects to be accrued.

If applicable, distinguish between the number of subjects who are expected to be enrolled and screened, and the number of subjects needed to complete the research procedures (i.e., numbers of subjects excluding screen failures.)

We plan to enroll 30 participants.

8.2 Sample size determination

If applicable, provide a justification of the sample size outlined in section 8.1 – to include reflections on, or calculations of, the power of the study.

The above sample size is based on resource constraints for a feasibility study. Only descriptive statistics will be calculated; therefore, a power analysis was not conducted.

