1.2 Primary Study Endpoints

State the primary endpoints to be measured in the study. Clinical trials typically have a primary objective or endpoint. Additional objectives and endpoints are secondary. The endpoints (or outcomes), determined for each study subject, are the quantitative measurements required by the objectives. Measuring the selected endpoints is the goal of a trial (examples: response rate and survival).

The objective is to determine the acceptability of the sip^{IT} tools for participants with a history of urolithiasis who seek to increase fluid intake as recommended by physician guidelines.

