2.0 Background

2.1 Scientific Background and Gaps

Describe the scientific background and gaps in current knowledge.

Complying with fluid consumption guidelines provides a variety of health benefits. Patients with a history of urolithiasis are a segment of the population that can benefit from meeting physician-recommended fluid consumption guidelines. Preliminary studies with this population have revealed patient interest in using various technologies (i.e., wrist-worn sensors, smart water bottles, mobile applications) to increase their fluid consumption but we are not aware of any that combine multiple technologies. Our long-term goal is to examine if just-in-time reminder notifications to drink following periods when patients have not been drinking will increase compliance among those with a history of urolithiasis. To prepare for that study, we seek to evaluate the feasibility and acceptability of the sip^{IT} tools in this study.

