3.3.2 Follow-up for withdrawn subjects

Describe when and how to withdraw subjects from the study; the type and timing of the data to be collected for withdrawal of subjects; whether and how subjects are to be replaced; the follow-up for subjects withdrawn from investigational treatment.

The researcher can withdraw a participant if they fail to wear the study-provided smartwatch for a period of 7 days. Non-wear will be determined by monitoring heart rate data from the smartwatch. Participants who are withdrawn will be replaced.

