7.0 Study Design and Procedures

7.1 Study Design

Describe and explain the study design.

Participants will be asked to fill out baseline questionnaires and height and weight will be measured at the beginning of the study. Additional questionnaire completion and interviews will take place at one month and three months. Participants will wear a Fitbit Versa smartwatch and use an H₂OPal water bottle (and install their associated mobile apps on the participant's personal smartphone) to track their fluid consumption over the entire three month study. If one of the measurement tools (i.e., self-monitoring in the H₂OPal app, the H₂OPal water bottle, the sip^{IT} watch app) does not detect a drinking event within 30 minutes, a text message prompting fluid consumption will be sent to the participant's smartphone and smartwatch. If one of the measurement tools detects drinking, no notification will be delivered.

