8.3 Statistical methods

Describe the statistical methods (or non-statistical methods of analysis) that will be employed.

Descriptive statistics will be employed to assess feasibility of using sip^{IT} tools for increasing fluid consumption guidelines as well as to assess participant acceptability of using the sip^{IT} tools.

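### Replacing participants withdrawn for not wearing the watch, with no analysis denominator defined, could inflate the primary acceptability result

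*Combined protocol and SAP*

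**What the plan says.** Section 1.2 gives the primary endpoint as an objective: "The objective is to determine the acceptability of the" sipIT tools in people with a history of urolithiasis. It names no instrument, summary measure, time point or analysis population.

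Section 8.1 states "We plan to enroll 30 participants", and 8.2 explains that "The above sample size is based on resource constraints for a feasibility study" and adds "Only descriptive statistics will be calculated; therefore, a power analysis was not conducted". Section 8.3 is one sentence: descriptive statistics will be used for feasibility "as well as to assess participant acceptability of using the" tools. No interval is mentioned.

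Section 3.3.2 lets the researcher withdraw a participant after 7 days without wearing the watch, judged from heart-rate data. It then says "Participants who are withdrawn will be replaced". The template prompt above that answer asks what data are collected from withdrawn subjects and when. The answer does not say.

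On timing, section 7.1 states "Additional questionnaire completion and interviews will take place at one month and three months". On purpose, section 2.1 describes a later study of reminder notifications and says "To prepare for that study, we seek to evaluate the feasibility and acceptability of the" tools.

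**The concern.** In an acceptability study, abandoning a device is itself an acceptability outcome. Wearing the watch is part of what is being evaluated. Someone who leaves it off for a week is more likely than average to find the tools burdensome. Section 3.3.2 allows that person to be withdrawn and brings in someone else, and nothing in 1.2 or 8.3 requires the withdrawn person to be counted.

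A team following the text could therefore report acceptability among the 30 people who stayed or were brought in, and omit those who stopped. That figure describes acceptability among people who tolerated the watch, whereas section 1.2 asks about participants with a history of urolithiasis who want to drink more. Without an interval, the reader also cannot see how imprecise a figure from about 30 people is.

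**Working it through.** **Inputs from the documents.** Planned enrolment 30 (8.1). Withdrawal possible after 7 days of non-wear, with replacement (3.3.2). The documents give no withdrawal rate, acceptability rate, confidence level, power or precision target, so the 30 has no calculation behind it to reproduce.

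**Assumptions.** Acceptability is summarised as a proportion. Intervals are 95% and exact (Clopper-Pearson). Each of *k* withdrawn people is replaced, so 30 are retained and 30 + *k* were ever enrolled. Among the 30 retained, 24 rate the tools acceptable.

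**Step 1: size of the bias.** Let *a* be acceptability among the 30 retained and *w* among the *k* withdrawn. The all-enrolled proportion is (30*a* + *kw*)/(30 + *k*). The retained-only figure exceeds it by

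bias = [*k*/(30 + *k*)] × (*a* − *w*).

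The bias is upward whenever the withdrawn are less accepting than the retained, and zero if the two groups are alike.

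**Step 2: all withdrawn counted as not accepting (*w* = 0, *a* = 24/30 = 0.80).**

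| Replaced (assumed) | Accepting / enrolled | Proportion | Exact 95% CI |
|---|---|---|---|
| 0 | 24/30 | 80.0% | 61.4% to 92.3% |
| 3 | 24/33 | 72.7% | 54.5% to 86.7% |
| 5 | 24/35 | 68.6% | 50.7% to 83.1% |
| 6 | 24/36 | 66.7% | 49.0% to 81.4% |
| 10 | 24/40 | 60.0% | 43.3% to 75.1% |

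For *k* = 6 the formula gives (6/36) × 0.80 = 0.133, the 13-point gap between 80.0% and 66.7%.

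**Step 3: less extreme cases, still with *k* = 6.** If half of the withdrawn found the tools acceptable, the all-enrolled result is (24 + 3)/36 = 75.0% (57.8% to 87.9%), a bias of (6/36) × 0.30 = 5 points. If all six did, it is 30/36 = 83.3% (67.2% to 93.6%), and the retained-only figure would be slightly too low. Counting the withdrawn as not accepting is therefore the pessimistic end of a range.

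**Step 4: what an interval adds.** At n = 30 an observed 20/30 (66.7%) has an exact interval of 47.2% to 82.7%, and 21/30 (70.0%) one of 50.6% to 85.3%. If the measure is a mean score, the 95% half-width is t(0.975; 29)/√30 = 0.37 SD. The reader needs this beside the estimate, whichever form the endpoint takes.

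**Step 5: why a fixed count would not work as a bar.** Suppose, for illustration only, that the lower 95% limit had to exceed 50%. With 30 enrolled that takes 21 (lower limit 50.6%). With 33 it takes 23 (51.3%), and with 36 it takes 25 (51.9%). With 36 enrolled, 21 gives a lower limit of only 40.8%. Once anyone is replaced, a count fixed for 30 no longer has its intended meaning.

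**The case against.** **This is a descriptive feasibility study.** Omitting a power analysis and setting the sample size by resources are coherent choices, and nothing here shows that 30 is wrong. That stands. The point asks for neither a power calculation nor more participants.

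**Non-wear is not the same as non-acceptance.** The rule concerns only the watch, while the tools also include a bottle and apps. Withdrawal is discretionary. Section 7.4.4 has staff contact participants after three days without a heartbeat or a message response, partly to check for safety or study issues, so some non-wear will have other causes. This stands too, and it is why two versions of the result should be shown.

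**The plan does not say withdrawn participants' data are dropped.** True. It does not say they are kept either, nor that a rating is sought from them. Replacement without a stated denominator leaves that choice until after the data are seen.

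**Descriptive statistics can include an interval.** They can, but the plan does not commit to one.

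**Stronger readings the documents do not support.** A reader might infer that the trial must settle a go/no-go decision and fails for lack of a threshold. Section 2.1 says only that the study prepares for a later one, and no go/no-go rule is stated. Whether a descriptive feasibility study needs a bar is debatable. A reader might also infer that acceptability is rated at both follow-up visits, so that the better one could be quoted. Sections 7.1, 7.2.3 and 7.2.5 mention unnamed questionnaires and interviews, and the instruments are not in the file. Repeated measurement is possible but not shown.

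**Conclusion.** The point holds for the denominator and the interval. The plan permits withdrawal for a behaviour plausibly linked to the primary outcome, replaces those withdrawn, and does not say whether they count. If they do not, the primary result is likely to be biased upward.

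The documents do not fix the size. With 80% acceptance among 30 retained participants and the withdrawn counted as not accepting, the overstatement is about 7 points for 3 replacements, 13 for 6 and 20 for 10. It is smaller if some of the withdrawn found the tools acceptable. These figures assume a binary endpoint and assumed numbers of replacements; the direction requires only that withdrawn participants are less accepting on average.

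The choice of primary visit is a conditional matter, relevant only if the same measure is taken at both visits. A progression bar is optional. Neither is a demonstrated fault in the plan.

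**What to change.** The withdrawal rule itself need not change. Make these changes before enrolment:

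- **3.3.2:** State that participants who are withdrawn and replaced remain in the analysis. Record the reason for withdrawal and seek an acceptability rating where the participant is willing.
- **1.2:** Name the acceptability measure and its summary (a proportion with its cut-point, or a mean score). If the same measure is taken at both visits, make Visit 3 the primary reading and the one-month visit supportive.
- **8.3:** Analyse everyone enrolled and report the number withdrawn for non-wear. Give the result with withdrawn participants counted as not accepting, beside the result in those who completed the rating. For a mean score, state in advance what value stands in for a missing rating in the first version. Attach a 95% interval to each, exact for a proportion and t-based for a mean.
- **If the sponsor wants a progression bar:** State it as a value the lower confidence limit must exceed, not as a count, because the number enrolled exceeds 30 once anyone is replaced.

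The cost is a few sentences and one or two extra lines of output, with no enrolment beyond what the replacement rule already implies. The drawback is that the reported figure may look less favourable, and the version counting withdrawals as not accepting will be too harsh where non-wear had unrelated causes. Showing both versions lets the reader see that range.

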8.3 Statistical methods

Describe the statistical methods (or non-statistical methods of analysis) that will be employed.

Descriptive statistics will be employed to assess feasibility of using sip^{IT} tools for increasing fluid consumption guidelines as well as to assess participant acceptability of using the sip^{IT} tools.

9.0 Confidentiality, Privacy and Data Management

For research being conducted at Penn State Hershey or by Penn State Hershey researchers only, the research data security and integrity plan is submitted using “HRP-598 – Research Data Plan Review Form Application Supplement”, which is available in the Library in CATS IRB (<http://irb.psu.edu>). Refer to Penn State College of Medicine IRB’s “Standard Operating Procedure Addendum: Security and Integrity of Human Research Data”, which is available on the IRB’s website. **In order to avoid redundancy, for this section state “See the Research Data Plan Review Form” in section 9.0 if you are conducting Penn State Hershey research and move on to section 10.**

For all other research, in the sections below, describe the steps that will be taken to secure the data during storage, use and transmission.

9.1 Confidentiality

9.1.1 Identifiers associated with data and/or specimens

List the identifiers that will be included or associated with the data and/or specimens in any way (e.g., names, addresses, telephone/fax numbers, email addresses, dates (date of birth, admission/discharge dates, etc.), medical record numbers, social security numbers, health plan beneficiary numbers, etc.).

If no identifiers will be included or associated with the data in any way, whether directly or indirectly, please indicate this instead.

Participants will be provided with an email address created by lab staff that will be used to link data and preserve confidentiality. Identifiable information (the names, email addresses and phone numbers of the participants) will be indirectly associated with the data via the master code list.

9.1.1.1 Use of Codes, Master List

If identifiers will be associated with the data and/or specimens (as indicated in section 9.1.1 above), describe whether a master record or list containing a code (i.e., code number, pseudonyms) will be used to separate the data collected from identifiable information, where that master code list will be stored, who will have access to the master code list, and when it will be destroyed.

If identifiers are included or associated with the data as described in section 9.1.1 above, but no master record or list containing a code will be used, it will be assumed by the IRB that the investigator plans to directly link the identifiers with the data.

Alphanumeric codes matching the lab-generated email accounts will be used to identify participants (e.g., PSUsipIT_01). A master list containing the alphanumeric codes will be used to separate the data collected from identifiable information (the names, email addresses and phone numbers of the participants). This list that matches the names and contact information along with the code numbers will be stored in the locked file cabinet of the locked office of the research project manager ([name]). Only the study team members responsible for consent will have access to that list. The list will be destroyed after return of study information to interested participants upon study completion.

9.1.2 Storage of Data and/or Specimens

Describe where, how and for how long the data (hardcopy (paper) and/or electronic data) and/or specimens will be stored. NOTE: Data can include paper files, data on the internet or websites, computer files, audio/video files, photographs, etc. and should be considered in the responses. Refer to the "Investigator Manual (HRP-103)" for information about how long research records must be stored following the completion of the research prior to completing this section. HRP-103 can be accessed by clicking the Library link in CATS IRB (<http://irb.psu.edu>).

Please review [Penn State's Data Categorization Project](#) for detailed information regarding the appropriate and allowable storage of research data collected according to [Penn State Policy AD71](#). Although the IRB can impose greater confidentiality/security requirements (particularly for sensitive data), the IRB cannot approve storage of research data in any way or using any service that is not permissible by [Penn State Policy AD71](#).

Paper consent forms and contact information sheets will be stored in a locked file cabinet of the locked office of the research project manager ([name]) for a period of three years after the end of the study.

De-identified data will be stored on a fileshare server developed by our software development team, West Arete. De-identified data is stored in a relational database and encrypted during transmission. The data is stored in servers which are virtual machines hosted at a major provider, dedicated solely to our application on a network that is shared with other unrelated hosts, and is protected by a host-based firewall with "default closed" policy. The security practices that are applied to the servers include antivirus protection, host-based intrusion detection, uptime monitoring, strong authentication (private key with strong password) logins, and the operating system security updates are monitored and applied nightly. Logs are monitored daily and there are encrypted off-site backups. The de-identified data will be stored indefinitely.

This study will be issued a Certificate of Confidentiality. Researchers will not disclose or provide any identifiable information without the subject's prior consent or where permitted according to NIH's Policy on Issuing Certificates of Confidentiality.

9.1.3 Access to Data and/or Specimens

Identify who will have access to the data and/or specimens. This information should not conflict with information provided in section 9.1.1.1 regarding who has access to identifiable information, if applicable.

Approved research team members who have completed CITI Training for Human Subjects Research will have access to de-identified sensor data, questionnaire responses and semi-structured interview responses. Our vendors (Fitabase and West Arete) will have access to de-identified data from the smartphone and mobile apps.

9.1.4 Transferring Data and/or Specimens

If the data and/or specimens will be transferred to and/or from outside collaborators, identify the collaborator to whom the data and/or specimens will be transferred and how the data and/or specimens will be transferred. This information should not conflict with information provided in section 9.1.1.1 regarding who has access to identifiable information, if applicable.

West Arete developed a server that the data will be stored on. West Arete will share the data stored on the server with the research team (i.e., [name], [name], [name], [name], and [name]).

The researchers do not plan to release identifiable information collected in the study. However, if researchers consider releasing identifiable information in the future, the individual or institution receiving the identifiable information will be made aware they are also subject to the requirements of subsection 301 (d) of the Public Health Service Act.

9.2 Subject Privacy

This section must address subject privacy and NOT data confidentiality.

Indicate how the research team is permitted to access any sources of information about the subjects.

Describe the steps that will be taken to protect subjects' privacy interests. "Privacy interest" refers to a person's desire to place limits on whom they interact with or to whom they provide personal information.

Describe what steps you will take to make the subjects feel at ease with the research situation in terms of the questions being asked and the procedures being performed. "At ease" does not refer to physical discomfort, but the sense of intrusiveness a subject might experience in response to questions, examinations, and procedures.

During the consent process, the researcher will emphasize that participants can decline to answer any questions they find intrusive or do any actions they are not comfortable with.

